7.1. General Statistical Considerations

All subject-related, efficacy-related, and safety-related data collected must be included in the statistical analysis. In the statistical tables, the subject number serves as the unique identifier for subjects in this study.

Statistical analysis will be performed using SAS software (version 9.4 or higher).

Baseline Definition: The last valid measurement or record taken prior to administration.

General Principles for Statistical Description: Quantitative indicators will be described by calculating the mean, standard deviation, median, minimum value, maximum value, lower quartile (Q1), and upper quartile (Q3). Categorical indicators will be described using the number of cases and percentage for each category. **General principles of statistical inference:** Statistical description and testing of data will be conducted based on the characteristics of the data, selecting appropriate descriptive measures and testing methods.

For comparisons between groups of quantitative data, paired t-tests or Wilcoxon rank-sum tests will be used; for comparisons between groups of categorical data, chi-square tests or Fisher's exact probability tests will be used; and for comparisons of ordinal data, Wilcoxon rank-sum tests will be used. All statistical tests are two-sided (unless otherwise specified), and a p-value less than 0.05 is considered statistically significant (unless otherwise specified). Unless otherwise specified, statistical descriptions and inferences based on follow-up visits include only data from scheduled visits. For baseline assessments and clinical significance evaluations, data from both scheduled and unscheduled visits should be included.

Principles for retaining decimal places: The minimum and maximum values retain the same number of decimal places as the original values. The mean and its confidence interval limits, median, Q1, and Q3 have one additional decimal place compared to the original values. The standard deviation has two additional decimal places. Percentages and their confidence interval limits retain one decimal place (but for efficacy analysis, two decimal places are retained). P-values should be retained with four decimal places. If the P-value is less than 0.0001, it should be

presented as ‘<0.0001’; if the P-value is greater than 0.9999, it should be presented as ‘>0.9999’. The decimal places of data in the checklist should be the same as those in the original data.

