This Statistical Analysis Plan (SAP) has been prepared for the clinical trial titled:

“A Multicenter, Randomized Controlled Clinical Trial to Evaluate the Interventional Value of Glycated Albumin (GA) in Glycemic Control for Patients with Type 2 Diabetes Mellitus”

sponsored by Asahi Kasei Pharma Corporation. This document provides a detailed description of the statistical analysis methods and procedures to be applied in the study.

The SAP is based on the Protocol Version 3.0 dated March 8, 2023, and the Case Report Form (CRF) Version 3.0 dated February 1, 2024.

2. Research Objective

The objective of this study is to verify the hypothesis that:

“Adjusting treatment regimens based on GA test results is more effective in helping patients achieve target average blood glucose levels (HbA1c).”

3. Research Design

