3.1. Research groups

Subjects will be randomly assigned to two groups:

- Intervention Group (Group A)
- Control Group (Group B)

Each group will consist of 100 subjects. Randomization will be performed using block randomization generated by SAS version 9.4 or later, ensuring reproducibility. Randomization letters will be used to assign eligible subjects in a 1:1 ratio to either Group A or Group B.

All subjects will receive antidiabetic treatment according to standard clinical practice. The use of sulfonylureas, glinides, insulin, or insulin analogs is prohibited in this study.

At the first follow-up visit (Month 1), GA will be measured for subjects in the intervention group. Based on the GA normalization principle, the investigator will adjust the treatment regimen accordingly. At Month 2 and Month 3, blood samples will be collected, and GA will be measured after the follow-up period,

but these results will not be used to adjust treatment and will be used only for statistical analysis.

Subjects in the control group will also have blood samples collected at Month 1, Month 2, and Month 3, with GA measured after the follow-up period for statistical analysis only.

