3.3. Sample size

Each group (Intervention and Control) will include 100 subjects.

The sample size was determined based on a preliminary single-center pilot study (n=40), which showed that the proportion of subjects achieving HbA1c < 7% after 3 months was 76.9% in the intervention group and 46.2% in the control group (p = 0.226).

Assuming:

- $\alpha = 0.05$ (two-sided significance level)
- Power = 0.8
- Effect size = 30% difference between groups

Considering factors such as:

- Follow-up completion rate in the pilot study (72.5%)
- Multicenter design

The target sample size was calculated to be 100 subjects per group.

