4.1.2. Secondary Endpoints

Secondary endpoints include:

- Proportion of subjects with HbA1c < 6.5% at Visit 5
- Proportion of subjects with HbA1c < 6.0% at Visit 5
- Change in HbA1c from screening to Visit 5
- Incidence and frequency of hypoglycemia
- Change in pancreatic β-cell function
- Change in insulin resistance
- Change in body weight
- Change in waist circumference
- Change in BMI

All secondary endpoints will be evaluated as changes from screening to the end of treatment (Visit 5), including absolute and percentage changes.

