7.2. Data processing methods

7.2.1. Advance withdrawl and missing data

All missing data will not be imputed.

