*** Proportion of participants with HbA1c < 6% at Visit 5 (baseline 84 ± 3 days)**

Calculate the number of participants, percentage, and 95% CI of participants with HbA1c < 6% at Visit 5 (baseline 84 ± 3 days) in the intervention group and control group, respectively. Calculate the 95% CI for the difference in proportions between the two groups (intervention group - control group) and use the chi-square test or Fisher's exact probability test to compare the proportions of participants with HbA1c < 6% between the two groups.

List the participants with HbA1c < 6% at visit 5.

*** Decrease in HbA1c at Visit 5 (baseline 84 ± 3 days).** Calculate the decrease in HbA1c for the intervention group and control group at visit 5 compared to the screening period, as well as the percentage change. Use t-tests or Wilcoxon rank-sum tests for intergroup comparisons. Among them, the percentage change in HbA1c at Visit 5 compared to the screening period = $(\text{HbA1c at Visit 5} - \text{HbA1c at the screening period}) / \text{HbA1c at the screening period} \times 100\%$.

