*** Changes in pancreatic β -cell function**

*** Changes in insulin resistance levels**

*** Body weight**

*** Waist circumference**

*** Changes in BMI**

For the above secondary efficacy endpoints, calculate the change values and percentage changes relative to the screening period at the end of treatment (V5). For continuous variables, use t-tests or Wilcoxon rank-sum tests for between-group comparisons.

Among these, Percentage change relative to the screening period at the end of treatment (V5) = (indicator results at visit 5 - indicator results at the screening period)/ indicator results at the screening period

The indicator results are the results of the above secondary efficacy endpoints.

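### SAP 7.1 prescribes a paired t-test between two independent arms (probably a drafting slip); separately, change in HbA1c could be adjusted for the screening value at no data cost

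*SAP*

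**What the plan says.** - **General rule (SAP 7.1).** "For comparisons between groups of quantitative data, paired t-tests or Wilcoxon rank-sum tests will be used".
- **Endpoint rules (SAP 7.4.2).** For the fall in HbA1c: "Use t-tests or Wilcoxon rank-sum tests for intergroup comparisons". For HOMA-β, HOMA-IR, weight, waist and BMI: "For continuous variables, use t-tests or Wilcoxon rank-sum tests for between-group comparisons". Neither mentions pairing. Protocol v2.0 section 5.6 also names only a t-test or rank-sum test.
- **Design (SAP 3.1).** "Subjects will be randomly assigned to two groups". Allocation is 1:1 in blocks, 100 per arm. No matching is described.
- **Scale of analysis (SAP 4.1.2).** Secondary endpoints are assessed as changes from screening to Visit 5, "including absolute and percentage changes".
- **Missing data (SAP 7.2.1).** "All missing data will not be imputed".
- **Adjustment.** The only adjusted analysis in the available text is the CMH test for centre on the primary endpoint (SAP 7.4.1). No continuous endpoint has a covariate.

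**The concern.** There are two points of different standing.

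**(a) Wrong as written.** A paired t-test works on within-pair differences. Groups A and B contain different people, and the plan defines no variable that could pair them. The sentence in 7.1 is also inconsistent within itself, since the rank-sum test offered as the alternative is for independent samples. Reading *paired* as referring to within-arm change does not help, because the sentence is expressly about comparing groups. In the available text 7.1 is the only place that gives the type of t-test, and it gives the wrong one. Someone who followed it would have to invent a pairing and drop the unpartnered subjects.

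**(b) A missed gain, not an error.** The unadjusted comparison of change is valid under randomisation. But HbA1c is measured at screening for eligibility and again at Visit 5, so adjusting for the screening value needs no new data and can narrow the interval.

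**Working it through.** **(a) Paired test on independent arms**

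Inputs: 100 per arm and 72.5% completion in the pilot (SAP 3.3); no imputation (SAP 7.2.1); two-sided 0.05 (SAP 7.1).

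1. *Can everyone be paired?* Let completers per arm be Binomial(100, p), independent between arms. The probability of equal counts is the sum over x of P(X = x)². This is 6.3% at p = 0.725, 5.9% at 0.65 and 9.4% at 0.90. At p = 0.725 the mean absolute difference is 5.0, so on average five subjects have no partner.
2. *Error rate and power.* Expected completers are 100 × 0.725 = 72.5 per arm, taken as 72. The two-sample test has 2 × 72 − 2 = 142 df (critical value 1.977). The paired test has 72 − 1 = 71 df (1.994). An effect with 80.0% power on the two-sample test has about 79.5% on the paired test. Simulated type I error is 5.1% for both.
3. *Dependence on the pairing.* A 72-per-arm normal data set was scaled to a chosen two-sample p-value and then paired at random 20,000 times.

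| Two-sample p | Share of pairings with p < 0.05 |
|---|---|
| 0.02 | 100% |
| 0.03 | 96% |
| 0.05 | 44% (central 95% of p-values: 0.028 to 0.079) |
| 0.08 | 3% |
| 0.10 | 0.2% |

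**(b) Adjustment for the screening value**

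The documents give no SD, no correlation and no target difference for HbA1c change, so the following are assumptions. Visit 5 SD is 1.0. The ratio k of screening SD to Visit 5 SD is 0.87 or 1.0. The value 0.87 is the SD of a uniform distribution over the 7.5% to 10.5% entry range in Protocol 3.1.2.3: 3/√12 = 0.87. The screening-to-Visit-5 correlation ρ is 0.2 to 0.7, and the true difference is 0.4 points.

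- Variance of the change score: k² + 1 − 2ρk
- Variance under ANCOVA: 1 − ρ²
- Ratio: (k² + 1 − 2ρk)/(1 − ρ²) = 1 + (k − ρ)²/(1 − ρ²). In large samples it is never below 1, and it equals 1 when ρ = k.
- 95% CI half-width: 1.96 × √(2 × variance/72)
- Power: Φ(0.4/√(2 × variance/72) − 1.96)

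Example, k = 0.87 and ρ = 0.5: the change variance is 0.7569 + 1 − 0.87 = 0.887 and the ANCOVA variance is 0.75, a ratio of 1.18. The half-widths are 0.31 and 0.28, and power is 72% and 79%.

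| ρ | Variance ratio (k = 0.87 to 1.0) | Half-width, change | Half-width, ANCOVA | Power, change | Power, ANCOVA |
|---|---|---|---|---|---|
| 0.2 | 1.47–1.67 | 0.39–0.41 | 0.32 | 48–53% | 69% |
| 0.5 | 1.18–1.33 | 0.31–0.33 | 0.28 | 67–72% | 79% |
| 0.7 | 1.06–1.18 | 0.24–0.25 | 0.23 | 87–90% | 92% |

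The SAP also tests percentage change, which already makes some use of the screening value. Simulated power (3,000 trials per scenario, uniform screening HbA1c, no centre effect):

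| ρ | Absolute change | Percentage change | ANCOVA |
|---|---|---|---|
| 0.2 | 52% | 59% | 68% |
| 0.5 | 71% | 76% | 77% |
| 0.7 | 89% | 91% | 91% |

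Cases with little or no gain:

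- ρ = k = 0.87: ratio 1.00.
- Ten centre terms added, ρ = 0.7, no true centre effect: simulated ratio 0.97 to 1.01.
- Equal SDs with ρ of 0.95 to 0.98, as weight, waist and BMI might show over 12 weeks: ratio 1.03 to 1.01.

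**The case against.** **On (a):** this is one wrong word with almost no practical effect. SAP 7.4.2 governs every continuous efficacy endpoint and does not call for pairing, and 7.1 itself asks for methods suited to the data. The re-pairing figures describe an analysis nobody could run without making up a pairing. The type of test might also be stated in text not available here: SAP 7.2.3, or the table shells and programming specifications that the SAP cites. This fairly limits the weight of the point, but the word is still wrong and should be corrected.

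**On (b):** this is a preference about secondary endpoints.

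- Against the planned percentage-change test, ANCOVA adds only 0 to 1 points of power from ρ = 0.5 upward. That stands.
- The SD ratios of 0.87 and 1.0 may flatter the gain. If screening HbA1c falls linearly in frequency across the entry range, its SD is 3/√18 = 0.71, and the ratios drop to 1.27, 1.06 and 1.00 at ρ of 0.2, 0.5 and 0.7. That also stands: the tabulated ratios are not lower bounds. The gain shrinks, but ANCOVA does not become worse in large samples.
- ANCOVA adds a further p-value per endpoint, and the available text has no multiplicity plan. This is a reason to name the main analysis for each endpoint in advance. It does not argue against adjustment.

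**Conclusion.** Both parts hold, and together they are minor.

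**(a)** SAP 7.1 names the wrong kind of t-test for independent arms and conflicts with 7.4.2. It is probably a drafting slip. The harm is an irreproducible p-value near 0.05, and it arises only if 7.1 is followed over 7.4.2. The SAP declares its basis as a later protocol than the one supplied ("The SAP is based on the Protocol Version 3.0 dated March 8, 2023"), so no claim is made about an unrecorded departure from the protocol.

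**(b)** Adjusting HbA1c change for the screening value is an optional improvement. Its size rests on assumed SDs, correlation and treatment difference. It is useful at weak correlation, modest at moderate correlation, and absent when the correlation is close to the ratio of the screening SD to the Visit 5 SD. For weight, waist and BMI it may serve consistency only.

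The primary chi-square or Fisher test and the CMH sensitivity analysis are untouched.

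**What to change.** **(a)** In SAP 7.1, replace *paired t-tests* with *two-sample (independent-samples) t-tests*. This costs one phrase and should be done whatever is decided on (b). Whether Protocol v3.0 needs the same edit cannot be judged from the documents supplied.

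**(b) Optional.** In SAP 7.4.2, analyse absolute change from screening to Visit 5 by ANCOVA with arm and screening value.

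- Start with HbA1c, and extend to the other continuous endpoints for consistency.
- Centre terms are optional and may cancel the gain.
- Report the adjusted difference with its 95% CI.
- Keep the planned t-test or rank-sum tests of absolute and percentage change as supportive.
- Use a log scale for the HOMA indices only where they are defined. HOMA-β needs fasting glucose above 3.5 mmol/L, so list any excluded values by arm.
- Record the addition in SAP 7.7 before database lock, or label it post hoc if made later.

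The cost is a few lines of SAS and one entry in 7.7, with no new data and no change to any primary analysis.

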7.2. Data processing methods

7.2.1. Advance withdrawl and missing data

All missing data will not be imputed.

7.2.2. Derived and converted data

Islet β -cell function; $HOMA - \beta = \frac{20 \times FINS}{(FPG - 3.5)}$;

Insulin resistance level. $HOMA - IR = \frac{FINS \times FPG}{22.5}$

Among these, FINS represents fasting insulin (units: μ U/ml), and FPG represents fasting blood glucose (units: mmol/L).

Diabetes Duration (days) = (Date of informed consent – Date of first diagnosis of type 2 diabetes) + 1.

Adherence (%) = Actual total dose taken (mg) (i.e., prescribed total dose \pm total dose taken in excess/omitted) / Prescribed total dose (mg) * 100%, rounded to one decimal place.

The total dose (including all medications taken by the subject) (mg)

= $\sum_{i=3A/3B}^5$ Single dose (mg) * Dosage frequency * (Start date of next prescription/Actual date of visit 5 – Start date of current prescription)

where the dosing frequency is once

daily, dosing frequency = 1;

dosing frequency is twice daily, dosing frequency = 2;

dosing frequency is three times daily, dosing frequency = 3;

dosing frequency is four times daily, dosing frequency = 4;

dosing frequency is every other day, dosing frequency = 0.5;

Administration frequency is once weekly, administration frequency = 1/7, for visits 3A/3B, 4, 5.

Missed/extra total dose (including all drugs taken by the subject) (mg)

= $\sum_{i=3A/3B}^5$ Missed doses since last visit/Total dose taken,

where is visit 3A/3B, 4, 5.

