5.4 Adherence Analysis

Statistical descriptions of medication adherence records for each visit during the entire treatment period will be provided.

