7.3.6 Treatment Compliance

Analysis will be based on the Full Analysis Set (FAS).

For medication adherence during each follow-up visit, the following four aspects are summarized:

1. Calculate the number of cases and percentage of each category of timely medication adherence for antidiabetic drugs since the last visit (never missed, rarely missed (no more than 3 times per week), frequently missed (3 or more times per week), almost never taken, and overdose).
2. Calculate the percentage of adherence and perform descriptive statistics on participants' adherence. Summarize the number of cases and percentages for each adherence category (<80%, 80%-120%, >120%).
3. Use the ATC4 classification according to the WHODrug GLOBAL (B3) C [V2024MAR] coding system to calculate the number of cases and percentages of antidiabetic drugs used at each visit, and provide a summary by center.
4. Using the ATC4 classification of WHODrug GLOBAL (B3) C [V2024MAR], calculate the number and percentage of cases for each category of polypharmacy (monotherapy, dual therapy, triple therapy) for antidiabetic drugs at each visit, and provide a summary by center. If the ATC4 classification is an oral combination antidiabetic drug, it should be counted as dual therapy.

List the medication usage list for diabetes treatment and the diabetes treatment regimen list.

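### One adherence percentage from mg pooled over all drugs can place a subject who never takes a low-mg drug in the 80%-120% band, provided the other drugs are taken.

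*SAP*

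**What the plan says.** SAP 7.2.2 divides the mg actually taken by the mg prescribed. The mg taken are the prescribed total, plus any excess or minus any omission. The prescribed total is headed "The total dose (including all medications taken by the subject) (mg" and the adjustment "Missed/extra total dose (including all drugs taken by the subject) (mg". Each prescription contributes dose × frequency factor × days, and everything is added across drugs. The factors run from four times daily down to weekly: "Administration frequency is once weekly, administration frequency = 1/7". No ratio per drug is defined. SAP 4.5 and 7.3.6 concern antidiabetic drugs, so the sum is read here as covering those.

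SAP 7.3.6 opens with "For medication adherence during each follow-up visit, the following four aspects are summarized". Its second item bands the percentage: "Summarize the number of cases and percentages for each adherence category (<80%, 80%-120%, >120" per cent. Its first item is a self-report category that is not split by drug and includes "rarely missed (no more than 3 times per week), frequently missed (3 or more times per week), almost never taken". Its third and fourth items count the drug classes in use and "each category of polypharmacy (monotherapy, dual therapy, triple therapy". Listings of medication use and regimens are also planned.

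Protocol 5.4 gives the purpose: "Statistical descriptions of medication adherence records for each visit during the entire treatment period will be provided". SAP 6 requires good compliance for the PPS but leaves the criteria to data verification.

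**The concern.** A percentage built from pooled mg reflects tablet strength as well as behaviour. Two patients who each drop one of two drugs can get very different values, depending only on which drug carries more mg. Over-use of one drug can also cancel non-use of another.

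This is relevant to the trial because SAP 7.3.6 expects dual and triple therapy. Under Protocol 3.3.4.2 the response to a raised GA result in Group A is to add a type of oral drug. A reader may well look at the compliance tables to see whether added drugs were taken, and the pooled percentage cannot answer that. If it were also used as the PPS compliance criterion, membership of that set would depend partly on tablet strength.

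**Working it through.** The plan states no figure to reproduce, so the SAP 7.2.2 formula is applied directly.

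**Inputs.** From the SAP: the formula and frequency factors (7.2.2) and the bands (7.3.6), with exactly 80% in the middle band. Assumed, because the documents give no doses: the share w of prescribed mg that belongs to the never-taken drug, and the rate r at which the other drugs are taken.

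**1. Other drugs taken as prescribed.** Adherence = (P - wP)/P = 1-w.
- w = 1%, 5%, 10%, 20% gives 99.0%, 95.0%, 90.0%, 80.0%: all in the 80%-120% band.
- w = 21%, 25% gives 79.0%, 75.0%: both below 80%.

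**2. Other drugs taken at rate r.** Adherence = r(1-w), which is at least 80% when w ≤ 1-0.8/r.
- r = 100%: limit 20.0%.
- r = 95%: 1-0.8/0.95 = 15.8%. A 20% share now gives 0.95 × 0.80 = 76.0%, below 80%.
- r = 90%: 1-0.8/0.90 = 11.1%.

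**3. Two drugs over the same days, smaller-mg drug skipped, the other taken in full.** Adherence = D1/(D1+D2).

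| mg ratio D1:D2 | Result | Band |
|---|---|---|
| 1:1 | 50.0% | <80% |
| 2:1 | 66.7% | <80% |
| 3:1 | 75.0% | <80% |
| 4:1 | 80.0% | 80%-120% |
| 10:1 | 90.9% | 80%-120% |
| 100:1 | 99.0% | 80%-120% |

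A ratio of at least 4:1 is needed. If the larger-mg drug is skipped at 4:1, the result is 1/5 = 20.0%.

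**4. Netting.** Take 3:1 over 28 days. Prescribed: 3 × 28 + 28 = 112 units. Skipping the smaller drug leaves 84/112 = 75.0%. Two extra daily doses of the larger drug add 6 units: 90/112 = 80.4%, now in band.

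**5. Per visit or pooled.** The limit on the share of prescribed mg is the same either way. Only the daily mg ratio that produces that share changes when the two drugs run for different numbers of days.

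**6. Self-report.** A wholly skipped once-daily drug is 7 missed doses a week and meets the frequently-missed category. A wholly skipped once-weekly drug is 1 a week and fits the rarely-missed category.

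**7. By drug.** In every case in steps 1 to 3, the never-taken drug has adherence 0.0%, whatever its mg.

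**The case against.** The strongest reply is that little depends on this percentage. It is descriptive, and it is not the only compliance output. The self-report item would usually flag a skipped daily drug, and listings are planned. What escapes both measures is essentially a skipped once-weekly drug, whereas Protocol 3.3.4.2 describes the GA-guided addition as oral. The 20% limit also assumes that the patient drops one drug and takes all the others in full, which is the case most favourable to the concern. No regimen in the documents is shown to reach 4:1. All of this stands, and it keeps the point small.

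It does not make the pooled ratio a sound measure. The self-report item is not by drug, and the class and regimen counts show what was in use, not how much was taken. Reading the formula's wording literally, so that a never-taken drug drops out of both sums, does not help: the result is then 100%.

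A by-drug rule could also sit in material not available here: the special data notes listed as SAP 7.2.3, the table shells or the programming specifications. That is possible, but such a rule would contradict the explicit pooled formula, and the two would have to be reconciled.

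A reader might go further and infer that non-use of drugs added after a GA result will routinely be hidden, or that the efficacy comparison is biased. The documents do not support either. They give no doses from which to judge frequency, they do not tie this percentage to any efficacy analysis, and nothing in them points to an imbalance between arms.

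**Conclusion.** The concern holds as a minor flaw in a stated rule. The adherence percentage weights drugs by prescribed mg and nets across them. A never-taken drug with up to 20% of the prescribed mg leaves the subject in the 80%-120% band if all other drugs are taken as prescribed. The limit is 15.8% or 11.1% if they are taken at 95% or 90%. For two drugs over the same days, with the other taken in full, this requires a mg ratio of at least 4:1.

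How often this happens is unknown. The FAS primary analysis is unaffected. An effect on the PPS would arise only if this percentage were adopted to judge good compliance, which SAP 6 leaves open. The practical consequence is that the bands cannot be relied on to show whether each prescribed drug was taken.

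**What to change.** In SAP 7.2.2, compute adherence separately for each antidiabetic drug, as mg taken over mg prescribed for that drug, with no netting across drugs. In SAP 7.3.6, band subjects by arm on their drug-level values, for example the lowest and the highest per subject. Both are needed, because a mean would net again: 0% and 200% average 100%. If a numeric compliance cut-off is adopted for the PPS, base it on the drug-level values.

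No new data are required, since SAP 4.5 already has the CRF record the drug name with the missed or excess dose and its unit. The cost is SAP wording and some extra programming. Fewer subjects may count as adherent, and the PPS may be smaller if a drug-level cut-off is used.
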